#### 3.2. SECONDARY OBJECTIVES

- Describe any safety issues related to biopsy acquisition or drug combinations,
- Describe genomic/transcriptomic aberrations seen in NSCLC.

### 3.3. SPRING STUDY DESIGN

For the triple combination tested, we will conduct a seamless Phase 1/2 trial to establish the safety of the regimen and to identify the recommended Phase 2 dose.

#### 3.3.1. The Phase 1

A Phase 1 study will be conducted to assess the safety of the triple combination and establish concentration of each of the agents:

All patients enrolled in the Phase 1 of the study will be treated with the tested combination until progression unless toxicity occurs earlier. Eligible patients will be those with advanced/metastatic disease NSCLC with a maximum of two prior lines of treatment. Patients with already documented druggable oncogenic aberrations (EGFR mutations, ALK rearrangements, ROS1 or MET exon 14 skipping mutations if available) will be excluded from the trial. All patients with adenocarcinoma histology must have documentation of results for druggable oncogenic aberrations (EGFR mutations, ALK rearrangements, and ROS1 when available) prior to enrollment on the study.

In the case of patients already treated on SPRING protocol who are later determined to have EGFR mutation or ALK translocation or ROS1 or MET exon 14 skipping mutations after SIMS analyses, they will be asked to re-consent.

Patients enrolled in the phase 1 study who receive the RP2D will also be included in the phase 2 efficacy assessment. All patients will undergo a tumor and normal tissue biopsy in order to obtain correlative genomic and transcriptomic data.

#### Safety assessments for administration of avelumab in combination with palbociclib and axitinib

- **Blood chemistry and hematology assessments:** must be performed at baseline, every week during the first cycle and then prior to each avelumab dose, at end of treatment visit and at 30 days post-treatment safety follow-up (+/- 3 days).
- Monitor carefully proteinuria
- **Urine or blood pregnancy test** for women of childbearing potential must be performed at baseline and at least every month during treatment.
- **Free T4 and TSH** must be performed at baseline and at least every 8 weeks during treatment and at end of treatment or 30 days post-treatment safety follow-up (if not performed in the previous 8 weeks). Treat hypothyroidism and hyperthyroidism according to standard medical practice to maintain euthyroid state.
- **Blood pressure should** be carefully monitored prior to initiating axitinib and after onset of the treatment, in particular after 4 days.
- Monitor carefully all risk to arterial or venous thromboembolic event.
- Monitor carefully active gastrointestinal bleeding. If any bleeding requires medical intervention, temporarily interrupt axitinib.
- Monitor symptoms of gastrointestinal perforation or fistula periodically throughout treatment with axitinib.
- **ECG** will be performed at the beginning of each treatment cycle (+/- 3 days).

During the phase 1, patients will be closely monitored as follows:

- Within one week before day 1 of administration of the drugs, a full clinical examination will be performed,
- During the first month, patients will be seen about every week,
- Afterwards about every two weeks,
- **Extended safety follow-up:** Given the potential risk for delayed immune-related toxicities, safety follow-up must be performed up to 90 days after the last dose of avelumab administration. The extended safety follow-up beyond 30 days after last study drug administration may be performed either via a site visit or via a telephone call with subsequent site visit requested in case any concerns noted during the telephone call.

### **Treatment Plan:**

Days	1 cycle of treatment																											
	Week 1							Week 2							Week 3							Week 4						
1	2	3	4	5	6	7	8	9	10	11	12	13	14	15	16	17	18	19	20	21	22	23	24	25	26	27	28	
Avelumab	X														X													
Axitinib	X	X	X	X	X	X	X	X	X	X	X	X	X	X	X	X	X	X	X	X	X	X	X	X	X	X		
Palbociclib	off	off	off	off	off	off	X	X	X	X	X	X	X	X	X	X	X	X	X	X	X	X	X	X	X	X		

**Avelumab** is administered at the study center via an intravenous perfusion  
**Axitinib (Inlyta®)** and **palbociclib (Ibrance®)** are taken orally at home

The phase 1 of the dual combination avelumab and axitinib has been done and RP2D of the combination has already been assessed (avelumab (10 mg/kg IV every two weeks -1/+3 days) and axitinib (5 mg po bid). These doses are used in the study JAVELIN Renal 101, a randomized phase 3 trial, referenced at US Clinical Trials website:

<https://clinicaltrials.gov/ct2/show/NCT02684006?term=avelumab+and+axitinib&rank=1>

In order to add the third agent palbociclib, the dual drug combination dose will be reduced and the third drug will be added: **n ~ 30 patients.**

Dose level -1	3 patients receiving avelumab (10 mg/kg IV every two weeks -1/+3 days) and axitinib (2 mg po bid) and palbociclib at 75 mg po daily (7 days off; 21 days on)
Dose level 1	3 patients receiving avelumab (10 mg/kg IV every two weeks -1/+3 days) and axitinib (3 mg po bid) and palbociclib at 75 mg po daily (7 days off; 21 days on)
Dose level 2	3 patients receiving avelumab (10 mg/kg IV every two weeks -1/+3 days) and axitinib (5 mg po bid) and palbociclib at 75 mg po daily (7 days off; 21 days on)
Dose level 3	3 patients receiving avelumab (10 mg/kg IV every two weeks -1/+3 days) and axitinib (5 mg po bid) and palbociclib at 100 mg po daily (7 days off; 21 days on)
Dose level 4	3 patients receiving avelumab (10 mg/kg IV every two weeks -1/+3 days) and axitinib (5 mg po bid) and palbociclib at 125 mg po daily (7 days off; 21 days on)

Important note (1)	
A new escalation will be performed after 4 weeks of observation of at least three patients at the previous level if no dose-limiting toxicity (DLT) is observed.
 
If there is DLT at a dose level (clinically relevant, grade 3 or 4 toxicity or inability to complete 50% of treatment administration due to AEs) in the first four weeks, three new patients will be included at the same level. If a second patient has dose limiting toxicity at that dose level, the dose level will be declared above the MTD and the next lower dose level will be expanded to six patients from three patients. The next lower dose level will be declared the MTD providing that no more than 1 patient of six has dose limiting toxicity (or < one third of patients have DLTs). Once the presumed MTD is found, this dose will be set as the RP2D and the first part of the phase 2 study begins. Bayesian toxicity monitoring will be performed throughout the phase 2 study to ensure that the DLT for the tri-therapy is no more than 33% with high confidence. If greater than or equal to one third of patients have DLT, then next lower dose is MTD and that dose will be expanded in the same way.

Important note (2)	
The Clinical Monitoring Committee (CMC) constituted by all principal investigators will meet at least monthly by teleconference to discuss the patients included in the study, with the purpose of monitoring and managing any toxicity related issue.

Important note (3)	
A key point will be to understand the contribution of each of the drugs in generating toxicities. To this purpose, the CMC will specifically investigate whether observed toxicities relate to overlapping effects (such as fatigue, nausea diarrhea) or specific toxicities (such as febrile neutropenia – palbociclib) or low platelets level (axitinib). Appendix 8 describes all observed toxicities and outlines common or specific toxicities. Main toxicities specific to each drug are summarized in Important note (5).
 
Rules in case of toxicity/dose modifications:
 
For any Grade 3 dose-limiting toxicity (see page 32 for dose-limiting toxicity definitions) that is deemed to be drug specific, that drug will be held until resolution to <Grade 1. The drug will then be restarted with the dose at the next lowest level. If Grade 3 or greater toxicity recurs, the drug will be permanently stopped. Exception is hematologic toxicity which may be handled as in Important note (5), palbociclib section or Important note (6).
 
If a toxicity has been deemed to be due to a single drug, but persists at <math>\geq</math> grade 3 level after stopping the drug, all drugs will be stopped.
 
If it is unclear as to the drug that is causing a toxicity, all three drugs will be held.

	
Toxicities that may be clearly attributable to avelumab include immune toxicities such as immune mediated pneumonitis, hepatitis, colitis and nephritis, and infusion related reactions.
 
Toxicities clearly attributable to axitinib include hypertension and proteinuria.
 
Toxicities clearly attributable to palbociclib include lowering of white blood cells (WBC) or platelet counts.
 
For Grade 4 dose limiting toxicities, the drug to which it is attributable will be permanently stopped. If it is not clear as to which drug is associated with the toxicity, all drugs will be permanently stopped.
 
A Clinical Monitoring Committee (that includes site PIs) may be convened to help decide to which drug the toxicity is attributable.

Important note (4)	For dose interruption and reduction events, accurate medical administration records will be maintained to capture changes in dosing regimens, including concomitant medications.

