For the triple combination, the starting dose of each agent of the dual combination will be reduced in order to add the third agent. Doses will then be progressively increased with, at each dose escalation, 3 new patients being added. Patients will be closely monitored to detect any adverse event until the MTD of the triple combination is determined or reaching the highest dose level of each agent, whichever occurs first. Note that if the MTD is reached, this dose combination is the RP2D.

- Specific safety measures related to administration of avelumab will be implemented in each participating center: specific inclusion/exclusion criteria, safety assessments (pregnancy testing, monitoring of free T4 and TSH), premedication in order to mitigate avelumab infusion-related reactions, administration of avelumab in a facility that enable immediate access to emergency care unit, extended follow up to 90 days following the last administration of avelumab, monitoring of all specific adverse events, and reporting to the Pharmacovigilance Unit of the sponsor, within 24 hours of any serious adverse events. For simultaneous administration with palbociclib and axitinib, other specific safety measures will be implemented (for example careful monitoring of arterial tension, bleeding, assessment of risk of arterial and venous thromboembolic events

relating to administration of axitinib, and careful monitoring of hematologic toxicities relating to administration of palbociclib). These specific measures are presented in a detailed manner in this protocol, at each concerned section/chapter; as well as in a specific [appendix 6](#).

- The study will then be expanded to a phase 2 in order to confirm the safety profile and assess the clinical utility of the tri-therapy approach in the treatment of metastatic NSCLC. All patients included in phase 2 will be receiving the tri-therapy combination at the RP2D, and will be followed up to determine clinical response, duration of the response and overall survival. Patients enrolled in the phase 1 study who receive the RP2D will also be included in the phase 2 efficacy assessment.

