Patients who have a dose limiting toxicity and it is unclear as to which drug may have caused the toxicity, may restart drugs at the next lower dose level once toxicity returns to  $\leq$  Grade I. If the investigator deems the toxicity to be due to one of the drugs in the regimen, only that drug may need to be reduced to the next lower dose level. A second dose reduction of this type may occur if toxicity recurs. For a patient who is responding (PR or CR) the investigator may continue to reduce the dose to the lowest dose level tolerable; for these responding patients, if one drug is deemed responsible for recurring serious toxicity, it may be stopped and the other two drugs continued after review by the clinical monitoring committee.

### 3.3.2. The Phase 2

When the recommended Phase 2 dose is reached, there will be a first expansion of the study to explore efficacy of the tested triple combination. In the expansion, only patients with unresectable or metastatic NSCLC with no prior treatment line will be treated. Up to 100 patients will be treated with the combination (~120 patients enrolled\*) until progression. For ethical reasons, even patients who failed biopsy(ies) will be treated with the triple-therapy. Pending clinical activity, the study may be extended (with a study amendment) to an additional 100 patients treated in phase 2 in order to attain sufficient statistical power to support the validity of the approach.

Study participation will be offered to patients with locally advanced or metastatic disease. Patients with documented oncogenic aberrations (EGFR, ALK, ROS1 if available, MET exon 14 skipping if available) at enrollment will be excluded from the trial. In the case of patients already treated on SPRING protocol who are later determined to have EGFR mutation or ALK translocation or ROS1 or MET exon 14 skipping mutations after SIMS analyses, they will be asked to re-consent. Patients will be included in the study regardless of their PD1 or PD-L1 expression status. Main outcome variables will include response rate (RR), progression-free survival (PFS), and overall survival (OS).

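### The general restart rule after a Grade 3 DLT is wrong for avelumab, and its stop-on-recurrence clause conflicts with the Dose reduction paragraph

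*Combined protocol and SAP*

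**What the plan says.** The Treatment Plan table in section 3.3.1 defines five dose levels, each a three-drug combination. Avelumab is 10 mg/kg every two weeks at all of them. Level 4 adds "axitinib (5 mg po bid) and palbociclib at 125 mg po daily (7 days off; 21 days on").

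Important note (3) sets the general rule. After any Grade 3 DLT attributed to one drug, that drug is held, and then: "The drug will then be restarted with the dose at the next lowest level". If Grade 3 or greater toxicity comes back, the drug is stopped permanently. The only exception is hematologic toxicity, which is sent to the palbociclib section of note (5) or to note (6).

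The Dose reduction paragraph at the end of section 3.3.1 covers the same ground. If the cause is unclear, patients "may restart drugs at the next lower dose level". If one drug is blamed, "only that drug may need to be reduced to the next lower dose level". It continues: "A second dose reduction of this type may occur if toxicity recurs". For responders it allows further reductions and adds that "if one drug is deemed responsible for recurring serious toxicity, it may be stopped and the other two drugs continued", after committee review.

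Avelumab also has its own rules, in the avelumab part of section 3.3.1 and in Appendix 6, Tables 2 to 4. These advise against dose reduction and set out, by toxicity and grade, when to withhold, resume or stop.

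**The concern.** A general rule that covers any drug-specific Grade 3 DLT, with one named exception, applies to avelumab as written. It tells the site to restart at a lower level that does not exist, and for some events to restart where another part of the protocol forbids any further dose. No sentence says which text prevails.

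The recurrence texts raise a similar problem. A site facing a second Grade 3 event can find support for stopping the drug and for reducing it again.

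What is at stake is patient safety and uniform treatment across sites. For avelumab the wrong action is re-exposure after Grade 3 pneumonitis, a hepatic event or an infusion reaction. For the other drugs it is a different dose, or a different decision to continue, for the same event.

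**Working it through.** The plan states no figure for this point, so the check sets the rules side by side and steps through the dose table.

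**Avelumab at Grade 3.** The five toxicities are those note (3) gives as clearly attributable to avelumab. Note (3) says the same for each: hold, then restart one level down.

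| Toxicity | Avelumab-specific rule at Grade 3 | Source |
|---|---|---|
| Infusion reaction | Permanent stop | Section 3.3.1 avelumab text; Appendix 6, Table 3 |
| Pneumonitis | Permanent stop | Appendix 6, Table 4, pulmonary |
| Hepatitis | Permanent stop | Appendix 6, Table 4, hepatic |
| Colitis (initial event) | Withhold, resume after steroid taper | Appendix 6, Table 4, gastrointestinal |
| Nephritis | Withhold, resume after steroid taper | Appendix 6, Table 4, renal |

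The count is 3 of 5 permanent stops. A lower avelumab level exists for 0 of 5, because the dose is 10 mg/kg throughout. The hepatic row is narrower than it looks. The DLT definition excepts Grade 3 enzyme rises that settle to Grade 1 or less, or to baseline, before the next cycle. Note (3) does not reach those.

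**Recurrence.**

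| Recurrence after a drug-specific Grade 3 DLT | Note (3) | Dose reduction paragraph |
|---|---|---|
| Below Grade 3 | No stop required | Second reduction allowed |
| Grade 3 or greater | Permanent stop | Second reduction allowed; for responders, stopping is optional |

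The texts agree in the upper row and conflict in the lower one.

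**Size of the step (secondary).** Doses are from the Treatment Plan table. The combined reading takes the drug's dose at the level below. The per-drug reading takes that drug's next lower tested dose.

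| Level | Axitinib, mg bid | Combined | Per drug | Palbociclib, mg | Combined | Per drug |
|---|---|---|---|---|---|---|
| 4 | 5 | 5 | 3 | 125 | 100 | 100 |
| 3 | 5 | 5 | 3 | 100 | 75 | 75 |
| 2 | 5 | 3 | 3 | 75 | 75 | none |
| 1 | 3 | 2 | 2 | 75 | 75 | none |
| -1 | 2 | none | none | 75 | none | none |

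For axitinib the readings differ at 2 of 5 levels: a cut of (5 - 5)/5 = 0% against (5 - 3)/5 = 40%. After two steps, level 4 gives 5 mg (0%) or 2 mg, (5 - 2)/5 = 60%. Level 3 gives 3 mg (40%) or 2 mg (60%). For palbociclib they agree wherever a lower tested dose exists, and note (6) partly covers the 75 mg floor with alternate schedules.

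The wording points both ways. Note (1) uses the phrase for combined levels: "the next lower dose level will be expanded to six patients from three patients". Section 1.1 speaks per drug: "reaching the highest dose level of each agent". The Dose reduction paragraph uses it for all drugs and then, in the next sentence, for one.

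**The case against.** The strongest reply is that specific rules normally govern over a general note. The avelumab rules are detailed and prominent, note (5) is introduced as dose-modification guidance, and the Clinical Monitoring Committee reviews toxicity at least monthly. A careful site would follow Appendix 6. This limits how often harm would follow, but it does not remove the conflict: note (3) names its one exception, avelumab is not in it, and no order of precedence is written. It is also fair that the five toxicities are partly an illustrative list, so 3 of 5 describes the note's own examples and is not a rate.

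On recurrence, the Dose reduction paragraph could be read as meaning recurrence below Grade 3. That would reconcile the texts, but it is not stated, and the responder clause on recurring serious toxicity sits badly with it.

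Four stronger readings are tempting and not supported:

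- **A reader might infer that the protocol sends axitinib patients at levels 3 and 4 back to the dose that caused the event.** The text leans the other way. The Dose reduction paragraph speaks of one drug being reduced, note (5) says to reduce axitinib for persistent hypertension, and its palbociclib section resumes at the next lower dose. A per-drug cut is the likelier intent, and its steps can be read off the dose table.
- **A reader might infer that after a thromboembolic event note (3) is the only guide to restarting axitinib.** Note (5) adds that axitinib is unstudied within 12 months of an arterial event or 6 months of a venous one. Appendix 8 marks these events as axitinib-specific, but Appendix 3 lists pulmonary embolism for palbociclib. If the cause is unclear, all three drugs are held.
- **A reader might infer that Grade 4 hematologic DLTs fall outside the exception.** The exception carries no grade limit and points to a section with its own Grade 4 line. A clarifying sentence is optional.
- **A reader might infer an effect on the statistical design.** No sample size, endpoint or stopping boundary takes these rules as an input.

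**Conclusion.** The point holds for avelumab and for recurrence. As written, note (3) prescribes a restart that is impossible for avelumab at every dose level and contradicts a required permanent stop for three of the five toxicities it names. Its permanent stop on Grade 3 recurrence conflicts with the second reduction in the Dose reduction paragraph. The undefined step is a lesser drafting gap, confined to axitinib at levels 3 and 4.

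Only patients with a drug-specific Grade 3 DLT are affected, and the documents give no rate of these by drug for the triple combination, so the number cannot be estimated. The risk is a wrong restart or inconsistent dosing at some sites, not in every patient. I assume the rules carry into phase 2, because section 3.3.2 gives no others. The avelumab and recurrence conflicts would then apply to the up to 100 patients treated there, whatever the recommended dose. The one-step axitinib gap would matter in phase 2 only if the recommended dose is level 3 or 4.

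**What to change.** In an amendment:

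1. Exclude avelumab from the restart sentence in Important note (3) and from dose-level reduction in the Dose reduction paragraph. Refer instead to the avelumab rules in section 3.3.1 and to Appendix 6.
2. Limit the second reduction in the Dose reduction paragraph to recurrence below Grade 3, so that it agrees with note (3). Name any exception meant for responders.
3. Define the step per drug: axitinib 5 to 3 to 2 mg bid, then stop; palbociclib 125 to 100 to 75 mg daily, then a note (6) schedule or stop. Cite this ladder where note (5) says to reduce axitinib.
4. Optionally, state that the hematologic exception in note (3) includes Grade 4 events.

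The cost is amendment text and a notice to sites. It adds no patients, visits or tests.

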**Important note (5):**

Below are the AEs specific to each drug, warnings/precautions and guidance for dose modifications/interruption of drugs.

**Palbociclib (IBRANCE):** (*reference USPI- IBRANCE*)

1. Capsules should be taken with food. Patients should be encouraged to take their dose of palbociclib at approximately the same time each day.
2. If the patient vomits or misses a dose, an additional dose should not be taken. The next prescribed dose should be taken at the usual time. Palbociclib capsules should be swallowed whole (do not chew, crush or open them prior to swallowing). Capsules should not be ingested if they are broken, cracked, or otherwise not intact.
3. It is known there is a potential for palbociclib to increase the exposure of axitinib through a time-dependent CYP3A4 mediated drug-drug interaction. As a weak time-dependent CYP3A4 inhibitor, palbociclib may reduce the clearance of axitinib, which may increase its exposure-related toxicities. Therefore, it is advised to: Exclude patients currently taking strong CYP3A4 inducers and inhibitors if an alternative concomitant medication cannot be used because they will increase the variability in PK for both axitinib and palbociclib, See [Appendix 9](#).
4. Exclude patients with moderate hepatic impairment from the dose escalation phase of the study or until the MTD for the combination regimen has been determined. The combined effect of CYP3A4 inhibition by palbociclib along with the reduced clearance observed in patients with moderate hepatic impairment on the PK of axitinib is unknown. See US package insert (PI) for axitinib for further details,
5. Exclude patients currently taking proton pump inhibitors from the study due to their impact on the disposition of palbociclib during the dose escalation phase. Patients taking H2-receptor blockers and local antacids can be included in the dose escalation portion of the study as these classes of agents do not alter the PK of palbociclib.
6. Grapefruit or grapefruit juice intake during the whole duration of the treatment should be avoided as it may increase concentration of the drug in blood.

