**Recurrent Grade 3 ADRs and Grade 3 infusion-related reaction require permanent discontinuation.**

**Any Grade 2 ADR should be managed as follows:**

- If a Grade 2 ADR resolves to Grade  $\leq$  1 by the last day of the current cycle, treatment may continue.
- If a Grade 2 ADR does not resolve to Grade  $\leq$  1 by the last day of the current cycle, infusions should not be given on the following cycle. If at the end of the following cycle the event has not resolved to Grade 1, it should be treated as a Grade 3 or 4 (except for hormone insufficiencies, that can be managed by replacement therapy; for these hormone insufficiencies, up to 2 subsequent doses may be omitted).
- Upon the second occurrence of the same Grade 2 ADR (except for hormone insufficiencies that can be managed by replacement therapy) in the same subject, treatment with avelumab has to be permanently discontinued.

Important note (6):	Specific protocol dose modification for toxicity management related to palbociclib: 

- In case of recurrent grade 3 hematologic toxicities, palbociclib may be reduced to 75 mg po daily one week off and one week on.

- In case of other severe (<math>\geq</math> grade 3) toxicity related to palbociclib, consider holding palbociclib until toxicity is grade 1 or less, then resume at the alternate schedule of 2 weeks OFF / 2 weeks ON.

----------------------------	---

- **DLT will be defined as:**

Any of the following events that are considered to be clinically significant and meaningful as per evaluation of the attending physicians and confirmed by CMC and at least possibly related to drug. DLTs for the purposes of dose-escalation will be evaluated during the 28-day period following the first dose of study treatment. Each treatment cycle is four weeks. Toxicities will be graded and documented according the NCI CTCAE (v4.03).

- **Non-hematological dose-limiting toxicity is defined as:**

- Persistent Grade 3 or 4 hypertension despite treatment with anti-hypertensive drugs.
- Grade 3 or 4 Gastrointestinal bleeding.
- Grade 3 or 4 Gastrointestinal perforation or fistula.
- Development of Reversible Posterior Leukoencephalopathy Syndrome.
- Persistent Grade 3 or 4 proteinuria.
- Grade 3 or 4 arterial or venous thromboembolic events.

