**TABLE 3. TREATMENT MODIFICATION FOR SYMPTOMS OF INFUSION-RELATED REACTIONS**

NCI-CTCAE Grade	Treatment Modification for avelumab
Grade 1 – mild Mild transient reaction; infusion interruption not indicated; intervention not indicated.	Decrease the study drug infusion rate by 50% and monitor closely for any worsening.
Grade 2 – moderate Therapy or infusion interruption indicated but responds promptly to symptomatic treatment (for example, antihistamines, NSAIDs, narcotics, IV fluids); prophylactic medications indicated for $\leq 24$ h.	Temporarily discontinue avelumab infusion. Resume infusion at 50% of previous rate once infusion-related reaction has resolved or decreased to at least Grade 1 in severity, and monitor closely for any worsening.
Grade 3 or Grade 4 – severe or life-threatening Grade 3: Prolonged (for example, not rapidly responsive to symptomatic medication and/or brief interruption of infusion); recurrence of symptoms following initial improvement; hospitalization indicated for clinical sequelae. Grade 4: Life-threatening consequences; urgent intervention indicated.	Stop avelumab infusion immediately and disconnect infusion tubing from the subject. Subjects have to be withdrawn immediately from avelumab treatment and must not receive any further avelumab treatment.

IV = intravenous; NCI-CTCAE = National Cancer Institute-Common Terminology Criteria for Adverse Event; NSAIDs = nonsteroidal anti-inflammatory drugs.

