### Pulmonary irAEs

Grade of Pneumonitis	Initial Management	Follow-up Management
Grade 1	Consider withholding avelumab therapy	Re-assess at least every 3 weeks  If worsens:

Radiographic changes only	Monitor for symptoms every 2 to 3 days Consider Pulmonary and Infectious Disease consults	Treat as Grade 2 or Grade 3 to 4.
Grade 2 Mild to moderate new symptoms	Withhold avelumab therapy Pulmonary and Infectious Disease consults Monitor symptoms daily, consider hospitalization 1.0 to 2.0 mg/kg/day prednisolone or equivalent followed by a corticosteroid taper. Add prophylactic antibiotics for opportunistic infections Consider bronchoscopy, lung biopsy	Re-assess every 1 to 3 days If improves: When symptoms return to Grade $\leq 1$ , taper steroids over at least 1 month and then resume avelumab therapy following steroids taper If not improving after 2 weeks or worsening: Treat as Grade 3 to 4.
Grade 3 to 4 Grade 3: Severe new symptoms; New / worsening hypoxia; Grade 4: life-threatening	Permanently discontinue avelumab therapy Hospitalize. Pulmonary and Infectious Disease consults. 1.0 to 2.0 mg/kg/day prednisolone or equivalent followed by a corticosteroid taper Add prophylactic antibiotics for opportunistic infections Consider bronchoscopy, lung biopsy	If improves to Grade $\leq 1$ : Taper steroids over at least 1 month. If not improving after 48 hours or worsening: Add additional immunosuppression (for example, infliximab, cyclophosphamide, IV immunoglobulin, or mycophenolate mofetil)
Hepatic irAEs		
Grade of Liver Test Elevation	Initial Management	Follow-up Management
Grade 1 Grade 1 AST or ALT $>$ ULN to 3.0 x ULN and/or total bilirubin $>$ ULN to 1.5 x ULN	Continue avelumab therapy	Continue liver function monitoring If worsens: Treat as Grade 2 or 3 to 4
Grade 2	Withhold avelumab therapy	If returns to Grade $\leq 1$ :

AST or ALT $> 3.0$ to $\leq 5$ x ULN and / or total bilirubin $> 1.5$ to $\leq 3$ x ULN	Increase frequency of monitoring to every 3 days	Resume routine monitoring, resume avelumab therapy If elevations persist $> 5$ to 7 days or worsen: Treat as Grade 3 to 4.

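### Important note (3) orders restart one dose level down after a first drug-specific Grade 3 DLT, which for avelumab contradicts the permanent-stop rules for four event types and names a dose step that does not exist

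*Combined protocol and SAP*

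**What the plan says.** The general rule is in Section 3.3.1, Important note (3). After a Grade 3 DLT judged specific to one drug, that drug is held until the toxicity resolves. Then: "The drug will then be restarted with the dose at the next lowest level". The permanent stop comes at the next event: "If Grade 3 or greater toxicity recurs, the drug will be permanently stopped". There is one carve-out, which begins "Exception is hematologic toxicity which may be handled as in" and goes on to name the palbociclib section of note (5) and note (6).

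The same note shows that avelumab is within its scope: "Toxicities that may be clearly attributable to avelumab include immune toxicities such as immune mediated pneumonitis, hepatitis, colitis and nephritis, and infusion related reactions".

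The avelumab rules are in Important note (5) and Appendix 6. Note (5) opens with "Below are the AEs specific to each drug, warnings/precautions and guidance for dose modifications/interruption of drugs". Its avelumab part, repeated in Appendix 6 Table 2, says: "Recurrent Grade 3 ADRs and Grade 3 infusion-related reaction require permanent discontinuation". Appendix 6 Table 3 says of a Grade 3 or 4 infusion-related reaction: "Subjects have to be withdrawn immediately from avelumab treatment and must not receive any further avelumab treatment". The Table 4 row for Grade 3 to 4 pneumonitis starts "Permanently discontinue avelumab therapy Hospitalize". The Table 4 rows for Grade 3 to 4 hepatic events and for immune-mediated myocarditis also order a permanent stop. Note (5) and Table 2 both advise against reducing the avelumab dose and offer delay or discontinuation instead.

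**The concern.** Read literally, note (3) places the permanent stop at the second Grade 3 event, while the avelumab rules place it at the first for certain events. A site applying note (3) alone could plan to re-expose a patient after an event for which the protocol's own safety tables rule out further avelumab. Because the note carves out only hematologic toxicity, a literal reader has grounds to think that avelumab's non-hematologic DLTs stay under the restart rule. Even where restart is allowed, the instruction to go down a level means nothing for a drug with a single dose.

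**Working it through.** This is a check of text against text. No sample size, power or error rate enters.

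**Step 1: avelumab dose by level (Section 3.3.1, Treatment Plan).** Levels -1, 1, 2, 3 and 4 give avelumab at 10, 10, 10, 10 and 10 mg/kg. Levels below 10 mg/kg: 0 of 5. By contrast, axitinib takes 2, 3 or 5 mg and palbociclib 75, 100 or 125 mg over the same levels. The step-down rule has content for the two oral drugs and none for avelumab.

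**Step 2: what each text orders at a first event.** Under note (3) the order is the same in every row: hold, then restart one level down.

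| Event | Route to DLT status (DLT definition, Section 3.3.1) | Avelumab rule | Conflict on permanence |
|---|---|---|---|
| Grade 3 infusion-related reaction | General line for other Grade 3 non-hematologic toxicity; the allergic-reaction line if judged allergic | Permanent stop (note (5); Appendix 6 Tables 2 and 3) | Yes |
| Grade 3 pneumonitis | Listed, from Grade 2 upward | Permanent stop (Table 4, pulmonary) | Yes |
| Grade 3 hepatic event | General line, unless it is an enzyme rise that recovers to Grade 1 or less, or to baseline, before the next cycle | Permanent stop (Table 4, hepatic) | Yes, for events that still count as DLTs |
| Immune-mediated myocarditis | General line, if Grade 3; not named in note (3) | Permanent stop, no grade condition (Table 4, cardiac) | Yes |
| Grade 3 colitis | General line | Withhold; may resume after an initial Grade 3 event (Table 4, gastrointestinal) | No; only the step-down fails |
| Grade 3 nephritis | General line | Withhold; may resume (Table 4, renal) | No; only the step-down fails |

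**Step 3: counts.** Event types with a permanent stop at the first event: 4. Of these, the rule names Grade 3 explicitly for 3; myocarditis is the ungraded fourth. Avelumab examples named in note (3): 5 (pneumonitis, hepatitis, colitis, nephritis, infusion reactions). In direct conflict: 3 of 5. For the other 5 - 3 = 2, resumption is allowed.

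**Step 4: time span.** For dose escalation, DLTs are assessed over 28 days, which hold two scheduled avelumab infusions (days 1 and 15; the next is due on day 29). Important note (1) and Section 7.3 also use the DLT for toxicity monitoring throughout phase 2. The conflict covers the first cycle on the narrow reading and the whole treatment period on the wide one.

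**The case against.** The strongest reply is that the specific rule governs. The toxicity-management paragraph in the avelumab part of note (5) sends sites to Appendix 6 Tables 2 to 4, and the introduction to Table 4 says immune-related events should be managed by that table. This covers pneumonitis, hepatic events and myocarditis; Table 3 covers infusion reactions in mandatory terms. A DLT must also be confirmed by the CMC. And since no lower avelumab level exists, re-exposure would mean giving the full 10 mg/kg, which note (3) does not order. All of this stands and limits the practical risk. It does not remove the inconsistency: none of these texts mentions note (3), and note (3) defers to note (5) only for hematologic toxicity.

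A reader might infer three stronger things that the documents do not support.

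- *That sites have no direction on avelumab toxicity.* They do, as just described. What is missing is a link between that direction and note (3).
- *That Table 4 contradicts the general avelumab rule by letting treatment resume after a first Grade 3 colitis.* Note (5) makes Grade 4 discontinuation permanent, drops that word for Grade 3, allows resumption on recovery, and makes recurrent Grade 3 permanent. Read together, these largely agree with the colitis row.
- *That Table 4 should therefore override the general Grade 2 and Grade 3 rules.* That would loosen the permanent stop at a second occurrence of the same Grade 2 reaction. It is a clinical trade-off, not a clarification.

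**Conclusion.** The inconsistency is real and confined to avelumab. Note (3) orders restart where the avelumab rules forbid it for four event types: three stated at Grade 3, plus myocarditis, which reaches note (3) only through its general wording. The hepatic case is narrowed by the liver-enzyme exemption. For other first Grade 3 events, such as colitis and nephritis, only the missing lower dose is at issue. The step-down is impossible at every one of the five levels.

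The conclusion assumes that an event is attributed to avelumab and confirmed as a DLT. The documents give no Grade 3 rates for these events, so no number of patients can be stated. Given the directions to the avelumab tables and the CMC review, this is an internal inconsistency with limited practical risk. It is worth correcting because it concerns re-exposure after serious toxicity and costs almost nothing to fix.

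**What to change.** Add to Important note (3), with a cross-reference in the dose-reduction paragraph of Section 3.3.1 (which is permissive but has no avelumab exception):

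> Toxicities attributed to avelumab are exempt from the restart-at-next-lowest-level rule and are managed by the avelumab section of note (5) and Appendix 6 Tables 2-4; where these require permanent discontinuation, avelumab is not restarted. Avelumab is delayed or discontinued, not dose-reduced.

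Two separate items can go with it, though neither adds weight to this point:

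- The ECOG exception in Appendix 6 Table 2 carries a *not* that reverses its meaning against note (5). Delete it: in a list of exceptions to discontinuation, only a change that does resolve makes sense.
- Note (5) and Table 2 stop avelumab at a second occurrence of the same Grade 2 reaction, while the Table 4 rash row allows it to resume after recurrent Grade 1 to 2 rash. Refer this to the sponsor's clinical team.

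The cost is a short exemption, one cross-reference and one deleted word, in the next amendment or a clarification letter. No extra data, visits or patients are needed.
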